SMC Review of Safety and PK Data from Step 1 (first 6 participants)

Safety, PK, and viral suppression data for the first 6 Step 1 participants will be reviewed within 8-10 weeks (**or as soon as is feasible in the event of Covid-19 related delays**) by the study team, sponsor, and SMC. (*No changes to the remainder of this paragraph.*)

Step 2 (all participants)

Following a successful Step 1 review, Step 2 may begin. Step 2 will begin after a participant has spent at least 8 weeks in Step 1 (**and has completed at least 2 consecutive dual bNAb infusion visits with the third or later dual bNAb infusion scheduled for the Step 2 entry visit**). (*No changes to the remainder of this subsection.*)

4. Section 6.2. 10-1074 Description, Supply, and Storage. The second sentence in the second paragraph has been revised to read:

10-1074 is supplied as single-use 20 mg/mL solution for IV injection in a 5ml **or 30ml** volume of buffered solution composed of sodium phosphate, potassium phosphate, potassium chloride, sodium chloride and polysorbate 80 with a pH of 7.0.

5. Section 6.3. Schedule of Intervention and Dosing. New text has been added after the second paragraph:

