2.1.8.1.1.2. Updated PK Considerations for VRC01LS in Step 1: Following the PK Step completion and PK data review, updated considerations for VRC01LS dosing in Step 1 are as below:

Participants in the VRC01LS arm received 30 mg/kg on Day 1, then 10mg/kg on Day 28 and 10mg/kg on Day 56 of the PK Step. The median (range) C_{max} after the first dose of 30 mg/kg was 710.7 mcg/mL (559.2—798.8 mcg/mL). The median C_{max} value fell to 429.2 mcg/mL and 453.5 mcg/mL after the second and third doses of 10 mg/kg. The median pre-dose (28 days post previous dose) concentrations were 223.3 mcg/mL (157.9-253.3 mcg/mL), 180.7 mcg/mL (164.9-227.1 mcg/mL) and 156.9 mcg/mL (125.8-201.4 mcg/mL) at Days 28, 56 and 84, respectively. Four of the six (67%) participants had VRC01LS concentrations above 200 mcg/mL at Day 28 while one had a concentration >200 mcg/mL at Days 56 or 84. However, all VRC01LS participants maintained VRC01LS concentrations above 125 mcg/mL throughout the study. The median AUC following the first dose (AUC_{0-28}) and across all three doses (AUC_{0-84}) were 7,983 mcg*d/mL (6,878-9,850 mcg*d/mL) and 22,247 mcg*d/mL (18,491-22,552 mcg*d/mL), respectively. All participants exhibited average concentrations (AUC divided by the collection duration) that exceeded 200 mcg/mL through Days 28 and 84 (Weeks 4 and 12) ([Table 1](#)).

Table 1. Median VRC01LS Concentrations for 6 Participants in the PK Step

Cmax _{Dose1} (mcg/mL)	Cmax _{Dose2} (mcg/mL)	Cmax _{Dose3} (mcg/mL)	Pre-Dose _{C28D} (mcg/mL)	Pre-Dose _{C56D} (mcg/mL)	Pre-Dose _{C84D} (mcg/mL)	AUC _{0-84D} (mcg*d/mL)
710.7	429.2	453.5	223.3	180.7	156.9	22,247

In summary, the VRC01LS troughs were somewhat lower than expected, and lower than the protocol-specified target trough concentration of 200 mcg/mL at 84 days. However, the peaks were adequate and there were no outlier values below the pre-specified value of 115 mcg/mL, and the average concentrations exceeded 200 mcg/mL through Days 28 and 84.

Following SMC review of these data on December 12, 2019, a recommendation was made to increase the maintenance dose of VRC01LS from 10mg/kg to 15 mg/kg to better match the adult values ([Figure 4](#); [Figure 5](#)). Therefore, in Step 1, VRC01LS will be initiated as a loading dose of 30mg/kg IV followed by 15mg/kg IV every 4 weeks.

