The VRC01LS concentration 28 days after the second dose (one loading dose of 30mg/kg and one maintenance dose of 15mg/kg), called the Concentration at Day 56 (C56D), will be used to assess adequacy of the dosing regimen. Specifically, if the median C56D of VRC01LS is above 160 mcg/mL (~80% of the original PK Step threshold of 200 mcg/mL accounting for 10-20% accumulation expected with continued dosing) then VRC01LS dosing will be deemed adequate from a PK perspective. If the PK data are above 160 mcg/mL and no dosing changes for VRC01LS are required, the dosing used in Step 1 will continue to be used for the remainder of the study unless new data emerges requiring additional review.

Figure 4. VRC01LS Concentrations in Children in the PK Step compared to Adult Values (Adult simulation data from VRC606)

[figure not shown]
[figure not shown]

Figure 5. Predicted VRC01LS Concentrations using Updated Maintenance Dose of 15mg/kg every 4 weeks

5. Section 2.1.8.2 PK Considerations for 10-1074: A new subsection heading **Initial Dosing Considerations for the PK Step for 10-1074**: has been added to the first paragraph to clarify

this subsection pertains to the PK Step only. (*No changes to the remainder of this subsection.*)

6. Section 2.1.8.2.1. Pharmacokinetic Targets for VRC01LS: A new subsection heading **2.1.8.2.1.1. 10-1074 target for the PK Step:** has been added to the first paragraph to clarify this subsection pertains to the PK Step only. (*No changes to the remainder of this paragraph.*)
7. A new subsection **2.1.8.2.1.2. Updated PK Considerations for 10-1074 in Step 1:** has been added as follows:

Following the PK Step completion and PK data review by the SMC, updated considerations for 10-1074 dosing in Step 1 are as below:

[figure not shown]

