Participants in the 10-1074 arm received 30 mg/kg on Days 1, 28 and 56. The median (range) Cmax after the first dose was 1,632.5 mcg/mL (1,174.0-1,998.6 mcg/mL). The median Cmaxs were in the same range after the second and third doses (1,484.6 and 2,063.6 mcg/mL). The median pre-dose (28 days post previous dose) concentrations were 155.2 mcg/mL (91.3-318.6 mcg/mL), 232.0 mcg/mL (113.6-328.5 mcg/mL) and 258.3 mcg/mL (122.4-467.3 mcg/mL) at Days 28, 56 and 84, respectively. All six participants had 10-1074 concentrations that greatly exceeded 7.5 mcg/mL throughout the study. The median AUC following the first dose (AUC₀₋₂₈) and across all three doses (AUC₀₋₈₄) were 11,461 mcg*d/mL (8,222-16,937 mcg*d/mL) and 37,505 mcg*d/mL (32,485-66,034 mcg*d/mL), respectively. All participants exhibited average concentrations that exceeded 250 and 350 mcg/mL through Days 28 and 84 (Weeks 4 and 12) ([Table 2](#); [Figure 8](#)).

Table 2: Median 10-1074 Concentrations for 6 Participants in the PK Step

Cmax _{Dose1} (mcg/mL)	Cmax _{Dose2} (mcg/mL)	Cmax _{Dose3} (mcg/mL)	Pre-Dose _{C28D} (mcg/mL)	Pre-Dose _{C56D} (mcg/mL)	Pre-Dose _{C84D} (mcg/mL)	AUC _{0-84D} (mcg*d/mL)
1,632.5	1,484.6	2,063.6	155.2	232.0	258.3	37,505

Following SMC review of these data on December 12, 2019, a recommendation was made to keep the 10-1074 dose the same at 30 mg/kg every 4 weeks for the remainder of the study.

Figure 8. 10-1074 Concentrations in Children in the PK Step compared to Adult Values (10-1074 adult percentiles from the Nussenzweig 584/MCA-906 study)

8. Section 2.3.1. Specific Aim 1 has been revised to read: VRC01LS and 10-1074 will not be associated with serious adverse events, and median trough concentrations at the doses used will be above established target values of 200 mcg/mL and 7.5 mcg/mL respectively.
9. Section 4. Study Design: The following subsections have been revised to read:

Step 1 (first 6 participants)

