2.1.8.1.1. Pharmacokinetic Targets for VRC01LS

The VRC01LS target, 3rd dose trough (C84D), is derived from the multiple-dose PK results from adults in VRC606 incorporating expected PK differences due to age and weight in the study population [45, 50, 51]. Adult trough concentrations following multiple doses of 20mg/kg every 12 weeks are 150-300 mcg/mL and predicted adult average steady-state concentrations are 400-550 mcg/mL. The target for acceptable C84D trough concentrations for this study corresponds to achieving C84D that are greater than adults following 20mg/kg IV every 12 weeks and which also corresponds to the majority of subjects having average VRC01LS concentrations at or slightly above those seen in the adults. The pediatric dose of 10mg/kg every 4 weeks is predicted to achieve similar average steady-state concentrations to adults (20mg/kg every 12 weeks) of about 500-650 mcg/mL. With more frequent every-4-week dosing, pediatric peak-trough fluctuation will be reduced. Thus steady-state troughs are expected to be 50% higher and C_{max} lower than adults receiving VRC01LS 20mg/kg every 12 weeks. With VRC01LS's very long half-life, it would take at least 6 months of "maintenance" dosing to reach steady-state and steady-state will not be achieved in the PK Step of this study. Therefore, VRC01LS will be initiated as a loading dose of 30mg/kg IV followed by 10mg/kg IV every 4 weeks to rapidly achieve concentrations near predicted steady-state. The VRC01LS concentration 28 days after the third dose (second 10mg/kg dose), C84D, will be used to assess adequacy of the dosing regimen. Specifically, if the median C84D VRC01LS concentration is above 200 mcg/mL (~80% of the predicted adult steady-state trough), then VRC01LS dosing will be deemed adequate from a PK perspective.

[figure not shown]
2.1.8.2. PK Considerations for 10-1074.

10-1074 has an average IC₅₀ of 0.37 mcg/ml among 182 sensitive strains tested. For 10-1074, target plasma levels for this study are based on adult data presented by Caskey et al. [23]. This open-label phase 1 clinical trial was performed among 14 HIV-uninfected and 19 HIV-infected individuals who received a single IV infusion of 10-1074 at doses of 3, 10 or 30 mg/kg. 10-1074 serum levels were

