Step 1 Week 8-32 Visits (if remaining in Step 1)

- Perform physical exam
- Adherence Assessment
- Acceptability Assessment (at Week 8)
- Continue ART while remaining in Step 1
- VRC01LS and 10-1074 given at Weeks 8, 12, 16, 20, 24, 28, 32
- Samples obtained for: HIV-1 RNA monthly (at Weeks 8, 12, 16, 20, 24, 28, 32); hematology, CD4/CD8, and LFTs (at Weeks 10, 14, 18, 22, 26, and 30); stored PBMC/plasma monthly (at Weeks 8, 12, 16, 20, 24, 28, and 32), qualitative HIV DNA PCR monthly (at Weeks 8, 12, 16, 20, 24, 28, and 32), whole genome sequencing (Week 8), quantitative HIV DNA PCR from stored PBMC every 8 weeks (at Weeks 8, 16, 24, and 32), immune profiling (at Weeks 8, 16, 20 (optional), 24, and 32), ELISA (at Weeks 8, 16, 24, and 32), PK testing (at Weeks 8, 12, 16, 20, 24, 28, and 32).

Step 2 Week 0 (must coincide with a Step 1 Week 8, 12, 16, 20, 24, 28, or 32 Visit)

- Perform physical exam
- Discontinue ART
- Adherence Assessment
- Acceptability Assessment
- VRC01LS and 10-1074 given
- Samples obtained for: HIV-1 RNA, CD4/CD8, stored plasma/PBMC, qualitative DNA PCR, whole genome sequencing, quantitative HIV DNA PCR from stored PBMC, immune profiling, ELISA and PK testing

Step 2 Non-infusion Visits (Weeks 1, 2, 3, 6, 10, 14, 18, 22)

- Perform physical exam (all visits)
- Samples obtained for: HIV-1 RNA (all visits), hematology (at Weeks 6, 10, 14, 18, and 22), CD4/CD8 (at Weeks 6, 10, 14, 18, and 22), LFTs (at Weeks 1, 6, 10, 14, 18, and 22), stored plasma/PBMC (only at non-infusion visits at Weeks 2 and 6), qualitative DNA PCR (all visits), immune profiling (optional at Week 2)

Step 2 Infusion Visits (Weeks 4, 8, 12, 16, 20)

- Perform physical exam (all visits)
- Acceptability Assessment (Week 12)
- VRC01LS and 10-1074 given
- Samples obtained for: HIV-1 RNA (all visits), stored plasma/PBMC (all visits), qualitative DNA PCR (all visits), quantitative HIV DNA PCR from stored PBMC (at Weeks 4, 8, 16), immune profiling (at Weeks 4, and 16, optional at Weeks 12 and 20), ELISA (at Weeks 4, 8, 16), PK testing (at Weeks 4, 8, 12, 16, 20)

Step 2 Week 24 Visit (or last visit off ART)

- Perform physical exam
- Acceptability Assessment
- VRC01LS and 10-1074 given (if visit at 24 weeks, but not if last Step 2 visit for rebound)
- Samples obtained for: HIV-1 RNA, CD4/CD8, stored plasma/PBMC, qualitative DNA PCR, whole genome sequencing, quantitative HIV DNA PCR from stored PBMC, immune profiling, ELISA, PK testing

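### The Day-56 VRC01LS gate of 160 mcg/mL does not follow from its stated 10-20% accumulation, so a median between 160 and about 167-182 does not support the Aim 1 trough target of 200

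*Protocol*

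**What the plan says.** For the PK Step, Protocol Section 2.1.8.1.1 placed the test after the third dose: "The VRC01LS concentration 28 days after the third dose (second 10mg/kg dose), C84D, will be used to assess adequacy of the dosing regimen". The median had to exceed 200 mcg/mL.

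Letter of Amendment #2, item 4 (Section 2.1.8.1.1.2) reports the six children given 30 mg/kg and then 10 mg/kg twice. The Day-28 median trough was 223.3 mcg/mL. The later medians and ranges were "180.7 mcg/mL (164.9-227.1 mcg/mL) and 156.9 mcg/mL (125.8-201.4 mcg/mL) at Days 28, 56 and 84, respectively". The letter calls these troughs "lower than the protocol-specified target trough concentration of 200 mcg/mL at 84 days", and the maintenance dose was raised to 15 mg/kg.

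For Step 1 the letter moves the test to the second-dose trough and lowers it. Dosing is adequate "if the median C56D of VRC01LS is above 160 mcg/mL (~80% of the original PK Step threshold of 200 mcg/mL accounting for 10-20% accumulation". If the gate is passed and no change is needed, the dose is kept for the rest of the study unless new data emerge.

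Item 8 of the same letter restates the Aim 1 hypothesis that "median trough concentrations at the doses used will be above established target values of 200 mcg/mL and 7.5 mcg/mL respectively". SAP Section 2.3.1 repeats it, with a bracketed note that the VRC01LS target became 160 at Day 56 of Step 1.

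**The concern.** A decision threshold comes with a numerical reason, and the reason does not give the threshold. The gate was also moved to an earlier trough and a lower value after the 10 mg/kg regimen had missed the old one. So it matters whether the new gate would have told that regimen apart from an adequate one.

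Passing the gate is one of several conditions for opening Step 2, where ART is stopped, and it fixes the dose for later children. The more lasting risk lies in reporting. A Day-56 pass could be cited as evidence that median troughs exceed 200, when the gate can be passed by exposure that falls well short of 200 one dose later.

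**Working it through.** **Inputs.** From Letter of Amendment #2, Section 2.1.8.1.1.2: gate 160, reference 200, accumulation 10-20%, and PK Step median troughs of 223.3 (Day 28), 180.7 (Day 56, range 164.9-227.1) and 156.9 (Day 84, range 125.8-201.4). From item 8: Aim 1 target 200.

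**1. The plan's figure.** 0.80 × 200 = 160. This reproduces.

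**2. The accumulation clause.**
- Forward from the gate: 160 × 1.10 = 176 and 160 × 1.20 = 192. Both are below 200.
- Back from the target: 200/1.20 = 166.7 and 200/1.10 = 181.8.
- Accumulation needed from 160: 200/160 − 1 = 25%.

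Taking 20% off 200 gives 160, but undoing a 20% rise means dividing by 1.20, which gives 167. The approximation sign does not help, because even the top of the stated range leaves 160 short.

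**3. The old regimen against the new gate.** At Day 56 on 30/10 mg/kg the median was 180.7 and the lowest child 164.9, so all six exceeded 160. At Day 84 the median was 156.9, a change of 156.9/180.7 − 1 = −13%. The stated accumulation would have predicted 180.7 × 1.10 to 180.7 × 1.20, that is 199 to 217.

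**4. How often the gate would pass that exposure.** Assume lognormal troughs with log-SD 0.126 to 0.20. The lower value is ln(227.1/164.9)/2.534, where 2.534 is the expected range of six standard normal values. The upper value is chosen to exceed the Day-28 and Day-84 estimates (0.187 and 0.186). Simulated medians of six give:

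| True median | Criterion | Chance of passing |
|---|---|---|
| 180.7 at Day 56 | above 160 | 91-98% |
| 180.7 at Day 56 | above 167 | 81-91% |
| 180.7 at Day 56 | above 182 | 46-48% |
| 156.9 at Day 84 | above 200 | below 1% |

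**5. What 15 mg/kg itself might give.** Assume dose-proportional kinetics and superpose the printed medians. Trough per mg/kg: f28 = 223.3/30 = 7.443; f56 = (180.7 − 10 × 7.443)/30 = 3.542; f84 = (156.9 − 74.43 − 35.42)/30 = 1.568.
- Day 56 at 30/15: 30 × 3.542 + 15 × 7.443 = 217.9.
- Day 84: 30 × 1.568 + 15 × (7.443 + 3.542) = 211.8.

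Setting the 10 mg/kg Day-84 median to 150 or 175, both inside its printed range, moves the 15 mg/kg Day-84 value to 204.9 or 229.9. Fitting instead to the printed AUC over 84 days gives 235.9 at Day 56 and 243.0 at Day 84. All four versions lie above 200. The change from Day 56 to steady state runs from −10% to +14% across them, so the printed data do not settle whether troughs accumulate at all.

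**6. Where a suitable trough exists.** Under Letter of Amendment #3 (Section 4, Step 2) children enter Step 2 "with the third or later dual bNAb infusion scheduled for the Step 2 entry visit". Protocol Section 7.7.1 then schedules "PK testing (at Weeks 4, 8, 12, 16, 20" of Step 2. The Step 2 Week 4 pre-dose trough therefore follows a third or later dose. For Step 1b (doses at Weeks 0, 4 and 8, with Week 8 as Step 2 entry) it falls at Week 12, which is Day 84. For Step 1a it comes after many more doses, because SAP Section 4.1.3 puts their Step 2 entry at Step 1 Week 32.

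**The case against.** The gate was written for 30/15 mg/kg, not 30/10. The fall from Day 56 to Day 84 on 10 mg/kg partly reflects washout of a load three times the maintenance dose, and it does not carry over directly to a load of twice the maintenance dose. The sponsor's own 15 mg/kg prediction (Figure 5) is not shown. If the true Day-56 median at 15 mg/kg is 218 to 236, as in step 5, a median of six lands between 160 and 182 in at most about 2.5% of draws under the same lognormal assumption. This stands: the fault bites in a region that the available model calls unlikely.

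The value 200 is also an exposure-matching target, about 80% of a predicted adult steady-state trough, and not an efficacy limit. The gate serves to confirm exposure under dual dosing and can still flag a large drop. The SMC reviews safety and viral suppression too, and troughs continue monthly. These points limit the consequence. They do not repair the rationale, since the letter itself ties 160 to 200 through accumulation.

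A reader might infer that no Day-56 pass could support 200. The documents do not support that: above about 182, the stated 10-20% does project to 200 or more.

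A reader might also infer that the SAP leaves the trough analysis without a target. Section 4.2.3 item 2 names no number, and items 1-2 omit Step 1a troughs after Week 8. But Section 2.3.1 gives 200, 7.5 and the 160 revision, item 1 reports monthly medians in Step 2, Section 1.1 sends detailed table outlines to an implementation plan not provided, and Sections 1.1 and 2.2 say Step 1a PK was handled earlier. That is mostly missing detail.

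**Conclusion.** The point holds for the cut-off. On printed numbers alone, 160 does not follow from 10-20% accumulation toward 200, because the consistent range is about 167 to 182. The regimen that missed the target at Day 84 would have passed at Day 56. A Day-56 median between 160 and about 167 (if accumulation is 20%) or 182 (if 10%) is not evidence for the Aim 1 statement.

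The pass probabilities rest on lognormal troughs and a spread estimated from six children. The 15 mg/kg projections rest on superposed medians. Neither is needed for the main conclusion. It would be tempting to conclude that 15 mg/kg is too low. Nothing in the documents shows this, and every projection above puts its Day-84 median over 200. The error is minor in size but sits in a dosing decision rule and is cheap to correct.

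**What to change.** The Step 1a review has already been held (SAP Sections 1.1 and 2.5), so (a) corrects how the gate is described and (b) governs the final report.

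(a) Section 2.1.8.1.1.2: either drop the accumulation clause, describe 160 simply as 80% of the PK Step threshold, and add that the 10 mg/kg Day-56 data (median 180.7, range 164.9-227.1) would also have met it; or restate the value as 167-182, with 182 under the lower accumulation figure. Restating it as 167 alone would still pass the old regimen.

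(b) Final report: base the Aim 1 VRC01LS trough statement on third-dose-or-later troughs compared with 200, and not on the Day-56 pass. Use the Step 2 Week 4 pre-dose trough. Give n, the median and its 95% confidence interval, and show Step 1a (later-dose) children separately from Step 1b (Day 84).

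Optional clarifications: name the cut-offs in SAP Section 4.2.3 item 2 (160 and 200 for VRC01LS, 7.5 for 10-1074) and add Step 1a Weeks 12-28 to items 1-2.

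Cost: wording and one named comparison, with no new samples and no dose change. The statement may look less favourable, and children who rebound before Step 2 Week 4 contribute no value. If the true Day-84 median were 205 to 212, the median of 20 children would fall below 200 by chance in about 4% to one third of cases (same lognormal assumption). It should therefore be reported with its interval and not as pass or fail.

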SMC	Safety Monitoring Committee
TDF	tenofovir disoproxil fumarate
ZDV	zidovudine

1. PROTOCOL SUMMARY

1.1. Title: A Clinical Trial to Evaluate the Impact of Broadly Neutralizing Antibodies VRC01LS and 10-1074 on Maintenance of HIV Suppression in a Cohort of Early-Treated Children in Botswana

1.1.1. Short title: Dual bNAb Treatment in Children

1.2. Sample Size: Up to 40 children

[figure not shown]
1.3. Study Population:

- HIV-infected children enrolled in the Early Infant Treatment (EIT) Study who are at least 96 weeks of life and meet entry criteria;
- In the PK Step only, HIV-infected children who are not enrolled in the EIT Study who are at least 96 weeks of life and meet entry criteria

1.4. Participating Sites: Gaborone CRS #31833 and Francistown CRS #31891

1.5. Study Design: This study will be a phase I/II, multi-site clinical trial of dual treatment with two broadly neutralizing monoclonal antibodies (bNAbs), VRC01LS and 10-1074, offered to HIV-1 infected virally suppressed children. There will be 4 Steps in the protocol: PK Step, Step 1, Step 2, and Step 3. In the PK Step, antiretroviral treatment (ART) is continued and 12 study participants will undergo safety and PK testing, 6 for each bNAb used in the study (10-1074 and VRC01LS). In Step 1, ART is continued and dual bNAb treatment occurs, with PK confirmation of dual bNAb dosing for the first 6 participants in Step 1. In Step 2, ART is withdrawn and dual bNAb maintenance treatment occurs. In Step 3, dual bNAbs will be discontinued and participants will be re-started on ART.

Figure 1: Study Schematic

1.6. Study Duration: 56-98 weeks**1.7. Study Intervention:****PK Step**

The first 12 participants in the study will undergo the PK Step, to allow for detailed safety and PK assessment of each bNAb alone. In the PK Step, while continuing ART, participants 1, 3, 5, 7, 9, 11 will receive VRC01LS at Week 0, Week 4, and Week 8 as a single intravenous (IV) dose (30 mg/kg load, then 10mg/kg maintenance); safety and PK measurements will occur at end of infusion, 1 hour post-infusion, 1 day post-infusion, 1 week post-infusion, 2 weeks post-infusion, and 4 weeks post-infusion. Participants 2, 4, 6, 8, 10, 12 will receive 10-1074 at Week 0, Week 4, and Week 8 as a single IV dose (30mg/kg), and safety and PK measurements will also occur at end of infusion, 1 hour post-infusion, 1 day post-infusion, 1 week post-infusion, 2 weeks post-infusion, and 4 weeks post-infusion. In the PK Step, it is anticipated that all 12 participants will be from the Early Infant Treatment (EIT) Study; however, in the event that 12 participants from EIT are not available at the time the PK Step begins, participants 9-12 may be recruited from other virally suppressed HIV-infected children. These additional, non-EIT children would not be eligible for further study steps after completing the PK Step. In the event that a participant discontinues bNAb during the PK Step, the participant may be replaced to allow for PK data to be obtained from 12 participants total.

SMC Review of Safety and PK Data from PK Step

After all 12 PK Step participants complete the PK Step, safety, PK, and viral suppression data will be reviewed within 8 weeks by the study team, sponsor, and SMC (earlier review by the SMC may be triggered based on pre-specified safety parameters). Participants will not continue to be dosed with bNAbs while awaiting SMC review, but will continue ART. All PK data from the PK Step will be assessed based on pre-specified PK trough targets; peak values will be assessed, but primary guidance for peak values will be based on toxicity. The study team will determine if the pre-specified trough targets have been achieved, and present this information to the SMC. The SMC will review safety data utilizing pre-defined safety criteria. If safety criteria are met, and if the PK data are in the pre-specified range, approval to begin Step 1 may be granted by the SMC. If the dosing and frequency of bNAbs established in the PK Step is acceptable, it will continue to be used for the first 6 participants in Step 1 (see additional safety review below). If a change in dosing is recommended by experts on the study team (or by the SMC, if it does not accept the team's recommendation), adjustments will occur and IRB and study sponsor approval will be sought regarding required protocol changes prior to starting Step 1. The recommendations by the study team or by the SMC may include early termination of the study, if warranted by the safety/PK data, or a re-design of the study as approved by the study sponsors and regulatory boards.

Step 1 (first 6 participants)

All Step 1-3 participants must be from the EIT Study. After approval, Step 1 will begin for a maximum of 6 participants, all of whom will have participated in the PK Step (3 from each PK Step group), and all of whom will have been >12 weeks from last bNAb dosing. ART is continued throughout Step 1, and all participants receive both 10-1074 and VRC01LS. If dosing recommendations do not change based on the PK Step, a VRC01LS loading dose of 30 mg/kg will be given at the start of Step 1, followed by 10mg/kg dosing at each 4-weekly visit, and 10-1074 dosing will be at 30mg/kg at each 4-weekly visit. At Week 0, Week 4, and Week 8 doses of Step 1, PK testing for both bNAbs will occur prior to infusion, and at Weeks 0 and 4 only at end of infusion, 1 hour post-infusion, 1 day post-infusion, and 1 week post-infusion. Post-infusion PK blood draws will occur at the end of and 1-hour

after the completion of both infusions, if both are administered on the same day. HIV-1 RNA will be checked every 4 weeks in Step 1. The first 6 participants in Step 1 will continue in this Step, receiving both oral ART and dual bNAb infusions, until the second study team/SMC review occurs. This review of safety and PK data will occur within 8 weeks of the 6th participant's Week 8 PK sampling.

SMC Review of Safety and PK Data from Step 1 (first 6 participants)

Safety, PK, and viral suppression data for the first 6 Step 1 participants will be reviewed within 8 weeks by the study team, sponsor, and SMC. All PK data will be assessed by the study team based on pre-specified PK trough targets which are the same as those used in the PK Step. The review will confirm that PK targets are met during dual bNAb administration. Safety criteria will be reviewed by the SMC, also using the same criteria as for the PK Step. If safety criteria are met, and if the PK data for both bNAbs are in the pre-specified range, the SMC may approve entry into Step 2 for the first 6 participants and enrollment of additional participants into Step 1. If the PK data are in range and no dosing changes for the bNAbs are required, the dosing will continue to be used for the remainder of the study unless new data emerges requiring additional review. If a change in dosing is recommended by experts on the study team (or by the SMC, if it does not accept the team's recommendation), IRB and study sponsor approval will be sought regarding required protocol changes. The recommendations by the study team or by the SMC may include early termination of the study, if warranted by the safety/PK data, or a re-design of the study as approved by the study sponsors and regulatory boards.

Step 1 (all subsequent participants)

After approval to proceed is obtained by the SMC, additional participants will enroll directly into Step 1 and receive dual bNAbs and ART for 8 weeks. All study visits and follow-up will be the same as for the first 6 Step 1 participants, with the exception of PK testing; only trough PK testing will be required for these participants, beginning at Week 4 of Step 1.

Step 2 (all participants)

Following a successful Step 1 review, Step 2 may begin. Step 2 will begin after a participant has spent at least 8 weeks in Step 1. For the first 6 participants, Step 2 will begin at a scheduled bNAb dosing visit (i.e. 4 weeks from last Step 1 bNAb dosing), and for all subsequent participants it will begin at the 8 Week visit date for Step 1 (which becomes the Week 0 Step 2 visit). Participants with ongoing viral suppression throughout Step 1 will undergo withdrawal of ART and will continue maintenance 10-1074 (30mg/kg) and VRC01LS (10mg/kg) treatment for up to 24 weeks in Step 2. HIV-1 RNA will be checked at all visits in Step 2, which occur weekly from Weeks 1-4 in Step 2, and every 2 weeks thereafter. Qualitative HIV DNA will be checked at each visit by DBS. If a participant experiences a single viral rebound ≥ 400 copies/mL in Step 2, ART will be re-started (and VRC01LS and 10-1074 will be discontinued). A single viral rebound is defined as an HIV RNA result ≥ 400 copies/mL at any Step 2 visit, without need for confirmation. If HIV RNA becomes ≥ 400 copies/mL prior to the end of Step 2, all evaluations ordinarily scheduled at "Week 24" will be performed immediately prior to ART re-initiation. If HIV-1 RNA is ≥ 40 copies/mL but < 400 copies/mL, or if Qualitative DNA turns from negative to positive, virologic monitoring tests will be repeated weekly. Clinical examination will occur at each study visit.

Step 3 (all participants)

All participants will end Step 2 after 24 weeks, and enter Step 3. In Step 3, both 10-1074 and VRC01LS will be discontinued, and ART will be re-started. Follow-up visits in Step 3 will occur at 4,

12, and 24 weeks.

